19.1 Ethical conduct of the trial

The trial will be conducted in a manner consistent with all applicable regulatory authority and IRB/IEC regulations (e.g., International Council for Harmonisation [ICH] Guideline for Good Clinical Practice [GCP, CPMP/ICH/135/95], the Declaration of Helsinki [in its currently acknowledged version], for centers in the USA: IRBs [21 CFR 56], and Obligations of Clinical Investigators [21 Code of Federal regulations [CFR] 312]) as well as in keeping with applicable local law(s) and regulation(s). The investigator must also comply with all applicable privacy regulations (e.g., USA: Health Insurance Portability and Accountability Act of 1996 [HIPAA]; European Union: General Data Protection Regulation [\[25\]](#)).

Financial disclosure by the investigator(s) pursuant to 21 CFR Part 54 will be obtained.

19.2 Independent ethics committee or institutional review board

Before the initiation of the clinical trial, the final protocol, any amendments if applicable, the patient information sheet and consent form, as well as any additional documents which are required by national regulations and the IEC or IRB will be submitted to the competent IEC or IRB for review. A favorable opinion for the clinical trial must be obtained from the IEC or IRB before any patient is enrolled at a center.

If appropriate, any additional requirements imposed by the IEC or IRB will be followed. Amendments to the trial documents will be notified to, or approved by, the IEC or IRB before implementation, if applicable.

19.3 Patient information and consent procedure

Before any clinical trial-related activities are performed, the investigator (or authorized designee) must review the informed consent form and explain the trial to potential trial participants. The investigator must ensure that the patient is fully informed about the aims, procedures, potential risks, any discomforts, and expected benefits of the clinical trial. Before consenting, the patient must be left with ample time to consider and ask questions. It must be emphasized that participation is voluntary and that the patient has the right to withdraw from the clinical trial at any time without prejudice. The patient and the investigator must then sign and date the consent form before the conduct of any trial procedures.

A copy of the patient information and informed consent form will be given to the patients for their records. The rights and welfare of the patients will be protected by emphasizing to them that the quality of their medical care will not be adversely affected if they decline to participate in this clinical trial.

If amendments to the final trial protocol affect the patient's participation in the clinical trial (e.g., a change in any procedure), the patient information and informed consent form must be updated to incorporate this modification, and patients must agree to sign the amended form indicating that they re-consent to participate in the clinical trial.

For sites in the United States of America: The investigator will comply with all applicable state and federal requirements, including the requirement of the HIPAA Privacy Rule. The authorization to use and disclose protected health information for research is part of the informed consent form, and a signed copy of the informed consent form must be placed in the trial record. Patients from whom additional blood samples will be collected to immune cell subtyping for further research studies will have to provide their consent to that optional additional procedure in the ICF.

19.4 Insurance coverage

Insurance coverage for damages emerging from the clinical trial will be provided according to applicable legal requirements. During the informed consent procedure, the investigator must inform the patient accordingly. Insurance details will be provided to the patient within the patient information sheet.

19.5 Submission to authorities

Documents required for the trial application will be submitted to the responsible competent authority (CA). The trial will not start until this authority has authorized the trial. Amendments to the trial protocol or to any other documents that must be reviewed by the CA will also be submitted to the CA in accordance with the regulatory requirements. If applicable, approval of the amendment must be awaited before implementing any changes.

19.6 Patient confidentiality

The trial protocol, documentation, data, and all other information generated will be held in strict confidence. No information concerning the clinical trial, or the data will be released to any unauthorized third party without prior written approval of the Sponsor.

Personal patient data will be kept confidential in compliance with the General Data Protection Regulation [25], the HIPAA Privacy Rule, and other applicable international and national requirements.

The investigator must ensure that the confidentiality and anonymity of trial participants will be maintained and that their identities are protected from unauthorized parties. In eCRFs,

Confidential

compensation documentation, or any other documents submitted to the Sponsor or Sponsor's designee, patients must be identified only by their identification codes; it is not allowed to use their names, addresses, telephone numbers, or similar information. The investigator will keep the original of the Patient Identification Log (including complete name and date of birth of each patient) in his/her file. The investigator must maintain these documents in strict confidence.

To allow compliance with GCP, all patients will be asked for consent regarding the access to their personal clinical trial-related data for monitoring, audits, and inspections as well as regarding transmission and storage of their pseudonymous data; a respective statement will be part of the informed consent form. Professionals getting access to source data for monitoring, audits and inspections are bound to preserve strict confidentiality.

20 Criteria for premature termination of the trial and criteria for initializing and closing a trial center

20.1 Trial safety stopping criteria

The trial will be stopped during the early and potential additional safety analyses when the following stopping criteria are fulfilled:

- $\geq 10\%$ of patients experience at least one SAE Grade 3, or
- $\geq 5\%$ of patients experience at least one SAE Grade 4

As outlined in Section 15.1.1.3, any SAE requires an underlying event that is considered an AE. Please consider the definitions in Section 15.1.6 when potentially COVID-19 related clinical events are considered an AE.

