A continuous event with changing intensities will be considered as one event of the most severe intensity documented. A continuous event with a changing seriousness will also be considered as one event, but the start and stop date of the time the event is serious must be separately documented. Clearly separated episodes of an event will be considered as separate events.

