15.1.1.3 Serious adverse events

An SAE is any untoward medical occurrence that, at any dose:

- results in death
- is life-threatening
- requires inpatient hospitalization or prolongation of existing hospitalization
- results in persistent or significant disability or incapacity
- results in a congenital abnormality or birth defect

NOTE: The term "life-threatening" in the definition of "serious" refers to an event in which the patient was at risk of death at the time of the event; it does not refer to an event, which hypothetically might have caused death, if it were more severe.

Medical and scientific judgment will be exercised in deciding whether expedited reporting is appropriate in other situations, such as important medical events that may not be immediately life-threatening or result in death or hospitalization, but may jeopardize the patient or may require intervention to prevent one of the other outcomes listed in the definition above. These will usually also be considered serious.

Examples of such events are intensive treatment in an emergency room or at home for allergic bronchospasm; blood dyscrasias or convulsions that do not result in hospitalization; or development of drug dependency or drug abuse. In addition, new malignancies that occur during the participation in the trial are defined as important medical events and must be reported as SAEs.

An SAE requires that the underlying event is considered an AE as defined in Section [15.1.1.1](#).

Hospitalizations due to a surgery or procedure during the trial will not be considered an SAE if the surgery or procedure will be performed for a pre-existing condition and the surgery or procedure was planned prior to trial entry. However, if the pre-existing condition deteriorates unexpectedly during the trial (e.g., surgery performed earlier than planned), then the deterioration of the condition leading to hospitalization will be considered an SAE. Hospital admission for social, quarantine, or convenience reasons will not be recorded as SAE. Hospitalization and death due to COVID-19 are anticipated clinical events of the underlying disease and cannot be used as reason for SAE classification without an underlying AE leading to hospitalization or death (see also Section 15.1.6).

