15.1.2 Classification of adverse events

Classification of AEs will be performed by the investigator.

Causality

The causal relationship between the AE and the administration of the IMP or trial procedure will be assessed as follows:

- Related: Implies a reasonable possibility of a causal relationship between the event and the IMP or procedure. This means that there are facts (evidence) or arguments to suggest a causal relationship.
- Not related: Implies no reasonable possibility of a causal relationship between the event and the IMP or procedure. This means that there are neither facts (evidence) nor arguments to suggest a causal relationship.

Severity

The severity of AEs will be graded according to the National (US) Cancer Institute-Common Terminology Criteria for Adverse Events (NCI-CTCAE), Version 5.0. If not specifically defined in the NCI-CTCAE, the following grading applies:

Grade 1: mild; asymptomatic or mild symptoms; clinical or diagnostic observations only; intervention not indicated

Grade 2: moderate; minimal, local or noninvasive intervention indicated; limiting age-appropriate instrumental activities of daily living (ADL)*

Grade 3: severe or medically significant but not immediately life-threatening; hospitalization or prolongation of hospitalization indicated; disabling; limiting self-care ADL **

Grade 4: Life-threatening consequences; urgent intervention indicated

Grade 5: Death related to AE

Outcome categories

Recovered: The patient has fully recovered from the event or the condition has returned to the level observed at Baseline

Recovering: The patient has recovered from the event, but the condition has not returned to the level observed at Baseline

Not recovered: The event is ongoing at the time of reporting and the patient has still not recovered

Recovered with sequelae: As a result of the AE, the patient suffered persistent and significant disability/incapacity (e.g., became blind, deaf or paralyzed)

Fatal: The patient died due to the event. If the patient died due to other circumstances than the event, the outcome should be stated otherwise (e.g., not recovered or recovering)

Unknown: If the outcome is not known or not reported

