15.1.6 Handling of anticipated clinical events of COVID-19

Typical COVID-19-related symptoms present at Baseline (examples such as fever, dyspnea, viral pneumonia, or hypoxia) and continuing during the trial without clinically unusual worsening* are considered anticipated clinical events of the underlying condition and will not be collected as AEs. In addition, disease characteristics and severity will be regularly captured within the scope of the clinical status assessment. Death, hospitalization, and use of ventilation, ECMO, or dialysis due to COVID-19 or its complications (which all are recorded as clinical endpoints for this trial) are not considered AEs (see Section 15.1.2) and should not be considered medically significant events by itself for the assessment of SAEs.

Any clinically unusual worsening* of COVID-19-related disease symptoms present at trial inclusion and any clinically relevant changes in clinical laboratory parameters, vital signs or other findings during physical examination which are considered unusual for COVID-19 disease and where a relationship to drug treatment cannot be excluded should be recorded as AEs.

* “Unusual worsening” means that, in terms of type or severity of symptoms, time frame or symptom fluctuations, the course of the disease progression is different from that in most patients with the same general conditions (disease status, age, health status, concurrent diseases).

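### The automatic safety stopping rule counts Grade 3 and Grade 4 SAEs but not Grade 5, so a patient whose only SAE is fatal (and not due to COVID-19) does not count

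*Combined protocol and SAP*

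**What the plan says.** Section 20.1 sets a mandatory rule for the early safety analysis and any additional ones. The trial stops if 10% or more "of patients experience at least one SAE Grade 3, or" if 5% or more "of patients experience at least one SAE Grade 4". It then reminds the reader that "any SAE requires an underlying event that is considered an AE" and points to section 15.1.6 for events that may be COVID-19 related.

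The definitions behind the rule are these:

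- Section 15.1.2 grades severity from 1 to 5. Grade 4 is life-threatening. The fatal grade is separate: "Grade 5: Death related to AE".
- Section 15.1.1.3 makes an event serious if it "results in death". Hospitalization and death due to COVID-19 "cannot be used as reason for SAE classification without an underlying AE leading to hospitalization or death".
- Section 15.1.6 treats "Death, hospitalization, and use of ventilation, ECMO, or dialysis due to COVID-19 or its complications" as clinical endpoints and not as AEs.
- Section 15.1.1.1 gives the recording convention: "A continuous event with changing intensities will be considered as one event of the most severe intensity documented".

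Section 8.1 places the early safety analysis after 30 patients in Part 1 have completed Day 28. At US centers enrollment pauses at that point. It resumes if the stopping criteria are not met, and the IDMC then continues with its full safety review.

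**The concern.** A rule that stops a trial for life-threatening SAEs should also stop it for fatal ones. In both limbs the words *at least* govern the number of SAEs, not their grade, so the text reaches Grades 3 and 4 only. A fatal SAE with a cause other than COVID-19 meets the protocol's definition of an SAE and is within the rule's subject, yet it falls outside both counts.

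At stake is the one safety threshold in the plan that leaves no room for judgement. At US centers it also decides whether enrollment restarts before the full IDMC review is finished. The rule could be reported as not met while fatal, possibly drug-related events had occurred at a frequency that would have stopped the trial had those patients survived.

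**Working it through.** **Is the omission in the text?** The two limbs of 20.1 name Grade 3 and Grade 4. The scale in 15.1.2 has a distinct Grade 5. No other section adds Grade 5, or deaths, to the automatic rule.

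**Is it deliberate?** The protocol does remove some deaths from the rule, but only those due to COVID-19 (15.1.1.3 and 15.1.6). Section 15.1.1.3 keeps a death with an underlying AE as an SAE, and 20.1 refers back to that section. No reason is given for counting a life-threatening SAE but not a fatal one. The patient-level rule in 17.1 also names Grades 3 and 4 only. That is sensible there, because a patient who has died cannot be withdrawn; the same reason does not carry over to a rule for the whole trial.

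**Patient counts at the early analysis.** Inputs: n = 30 (section 8.1) and thresholds of 10% and 5% (section 20.1). The denominator is taken as all patients pooled, the plain reading of the rule.

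- Grade 3 limb: 0.10 × 30 = 3, so 3 patients (10.0%).
- Grade 4 limb: 0.05 × 30 = 1.5, so 2 patients (2/30 = 6.7%).

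| Events among 30 patients | Grade 3 limb | Grade 4 limb | Automatic stop |
|---|---|---|---|
| Two patients with a Grade 4 SAE | 0/30 | 2/30 = 6.7% | Yes |
| Two patients whose only SAE is fatal | 0/30 | 0/30 | No |
| Two Grade 4 events, one becoming fatal, if the recorded worst grade is counted | 0/30 | 1/30 = 3.3% | No |

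The third row is conditional. It applies only if the recording convention in 15.1.1.1 also governs the stopping count, and 20.1 does not say which grade is counted. A patient who dies but also had a separate Grade 3 or 4 SAE does count, through that other event.

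**Chance of an automatic stop.** The plan states no operating characteristics for this rule, so there is no figure to reproduce. The rates below are assumptions, because the documents give none. Each patient is assumed to have SAEs of at most one grade, with probabilities p3, p4 and p5, and X3, X4 and X5 are the multinomial counts among 30 patients.

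- As written: stop if X3 ≥ 3 or X4 ≥ 2.
- With Grade 5 added to the second limb: stop if X3 ≥ 3 or X4 + X5 ≥ 2.

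With fatal SAEs only, the second expression reduces to 1 − (1 − p5)^30 − 30·p5·(1 − p5)^29. At p5 = 2% this is 1 − 0.5455 − 0.3340 = 0.121 after rounding.

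| p3 | p4 | p5 | As written | With Grade 5 added |
|---|---|---|---|---|
| 0 | 0 | 1% | 0 | 0.036 |
| 0 | 0 | 2% | 0 | 0.121 |
| 0 | 0 | 3% | 0 | 0.227 |
| 0 | 0 | 5% | 0 | 0.446 |
| 2% | 1% | 0 | 0.057 | 0.057 |
| 2% | 1% | 1% | 0.057 | 0.140 |
| 2% | 1% | 2% | 0.057 | 0.244 |
| 2% | 1% | 3% | 0.057 | 0.354 |
| 5% | 2% | 0 | 0.288 | 0.288 |
| 5% | 2% | 1% | 0.288 | 0.376 |
| 5% | 2% | 2% | 0.288 | 0.469 |
| 5% | 2% | 3% | 0.288 | 0.557 |

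**Sensitivity to the denominator.** If the limbs were applied within each arm (assumed 15 patients per arm), they would need 2 patients and 1 patient. With p3 = 5% and p4 = 2%, the chance that either arm triggers is 0.63 as written and 0.73 with p5 = 1% and Grade 5 added. The levels change; the gap does not, because a patient whose only SAE is fatal still counts for nothing.

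**The case against.** The strongest reply is that such deaths would not go unseen. SAEs reach the sponsor within 24 hours (15.1.4), and survival status is recorded twice daily during treatment and again at Day 28 (Table 3). The IDMC sees unblinded safety data at 30 patients. Further safety analyses can be started at any time (8.1), and termination at IDMC request or for a potential health risk is provided for (20.2). All of this stands, and it limits the practical harm. But these routes are discretionary and carry no threshold, whereas 20.1 exists to remove discretion.

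A second reply is that the gap is narrow. The patient must have a fatal AE that is not a COVID-19 death and no Grade 3 or 4 SAE. One may also read a patient as having experienced a Grade 4 SAE if the event was life-threatening before it became fatal. That reading is open, since 20.1 is silent on it, and it is why the worsening case above is only conditional. It does not rescue deaths without a documented Grade 3 or 4 serious phase.

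Third, the fatal-event rates are invented for illustration. Section 5.2.5 reports no deaths among more than 500 people exposed to the active moiety. That population differs from hospitalized COVID-19 patients, so it does not bound the rate here, but it gives no support for the higher rates in the table. The probabilities show how the rule behaves; they are not forecasts.

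Finally, the IDMC charter was not available and may set a counting convention. It could settle practice, but the protocol's mandatory wording would still be wrong.

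**Conclusion.** The concern holds. As written, the rule stops the trial for two life-threatening SAEs among 30 patients, but not for two fatal SAEs when those are the patients' only SAEs. Where fatal non-COVID-19 events are the only SAEs, the chance of an automatic stop is zero at any rate. Adding Grade 5 to the second limb would make it 0.036 to 0.446 at assumed rates of 1% to 5%. The textual finding needs no assumption about rates. The probabilities rest on a pooled denominator, assumed event rates and at most one SAE grade per patient. The consequence is confined to the automatic rule and the US resume-enrollment step; no efficacy analysis is affected. It should be fixed.

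**What to change.** Reword the second limb of 20.1 so that the trial stops when *5% or more of patients have at least one SAE of Grade 4 or 5*, and use the same wording in the IDMC charter. Keep both thresholds and the exclusion of COVID-19 deaths in 15.1.6. If the sponsor means the Grade 3 limb to be cumulative, write *Grade 3 or higher* there as well; separate limbs are also coherent, so that is optional.

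The change is one phrase and needs no new data. Its cost is more frequent automatic stopping when fatal non-COVID-19 SAEs occur, and on the pooled reading events on placebo count too. Over assumed p3 of 0, 2% or 5% and p4 of 0, 1% or 2%, the chance of stopping at 30 patients rises by 0.03 to 0.11 with 1% fatal SAEs, by 0.10 to 0.22 with 2%, and by 0.19 to 0.33 with 3%. With no fatal SAEs the change has no effect.

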20.2 Other criteria for halting or terminating the trial

The Sponsor reserves the right to halt or terminate the trial at any time. Reasons for termination include but are not limited to:

- Potential health risk for the patients
- High withdrawal rate
- New scientific knowledge becomes available that makes the objectives of the trial no longer feasible or valid
- Insufficient enrollment of patients
- The IDMC requests termination of the clinical trial based on review of all clinical and laboratory data
- The Sponsor, Regulatory Agency or an IEC or IRB requests the termination of the clinical trial

20.3 Criteria for closing a trial center

A trial center may be closed for the following reasons:

- The center is unable to recruit sufficient patients within the agreed time frame
- The center does not respond to trial management requests
- Multiple significant protocol deviations or substantial non-compliance
- The approval of the IEC or IRB in charge of the clinical trial is permanently revoked
- Additional local criteria might be established by written agreements between the Sponsor and the trial center

The Sponsor will notify the relevant CA, IEC(s), IRB(s) and investigator(s) in writing about the termination of individual centers or the entire trial.

The investigator may terminate his/her participation prematurely. If the investigator decides to terminate his/her participation before the trial is completed, he/she will notify the Sponsor in writing stating the reasons for the early termination. In terminating the trial, the Sponsor and the investigator will ensure that adequate consideration is given to the protection of the patients' interests.

The investigator will notify the relevant CAs, IEC(s), or IRB(s) in writing, if required, submit a copy of that notification to the Sponsor and return all IMPs and all related trial material, as applicable, to the Sponsor. Concerned eCRFs will be archived at the site. Authorization to access and edit the eCRF will be removed from the investigator and all authorized delegates.

21 Trial protocol, documentation and archiving of data

21.1 Amendments to the protocol

Any change to the protocol concerning the purpose of the trial, the trial design, or the patient's eligibility can only be made in the form of a written amendment to the trial protocol. Such amendments must be discussed and signed by the Sponsor and the investigator before implementation.

Substantial amendments, i.e., amendments likely affecting to a significant degree

- the safety or physical or mental integrity of the patients of the trial
- the scientific value of the trial
- the conduct or management of the trial, or
- the quality or safety of any IMP used in the trial

will be submitted to the CA and IEC or IRB for approval and favorable opinion as required by applicable regulations. If such amendments affect the patient's participation in the clinical trial (e.g., a change in any procedure), the patient information and informed consent form must be updated to incorporate this modification, and patients enrolled at the time of implementation of the amendment must re-consent to their participation in the clinical trial.

Non-substantial changes, e.g., minor corrections of administrative nature and/or rephrasing, which do not meet the above criteria for being substantial, are considered editorial changes. The IEC or IRB and CA do not need to be notified of such minor corrections. Non-substantial amendments will be signed by the Sponsor only.

If new events occur related to the conduct of the trial or the development of the tested IMP that may affect the safety of the patients, the Sponsor and the investigator will take appropriate safety measures to protect the patients against any immediate hazard. The Sponsor will immediately inform the CA and IEC or IRB of the new events and the measures taken.

